### 18.1.1. **ALL TEAEs**

Incidence of TEAEs will be presented by SOC and PT for all TEAEs, related TEAEs, TESAEs, and related TESAEs. Incidence will also be presented by SOC and PT for highest severity. Summaries by SOC and PT will present SOC in alphabetical order and PT within the SOC in descending order of incidence in the any teduglutide (ANY TED) treatment group.

#### 18.1.1.1. Severity

Severity is categorized as mild, moderate, or severe. Adverse events with a missing severity will be classified as severe. If a subject reports a TEAE more than once within that SOC/PT, summaries by severity will only provide the highest severity classification of the subject for the corresponding incidence summaries by SOC/PT.

#### 18.1.1.2. Relationship to Teduglutide

Relationship, as indicated by the Investigator, is classed as “*not related*” or “*related*”. TEAEs

Document: \\quintiles.net\Enterprise\Apps\sasdata\SASa\sas\Shire\Teduglutide\ZXA48914\Biostatistics\Documentation\SAP\SHP633-303\_SAP\_Draft\_V1.0\_20171023

Author: [REDACTED] Version Number: Draft V1.2  
Version Date: 16Jan2018

Template No: CS\_TP\_BS016 – Revision 3  
Effective Date: 01May2012

Reference: CS\_WI\_BS005

Copyright © 2012 Quintiles Transnational Corp. All rights reserved.  
The contents of this document are confidential and proprietary to Quintiles Transnational Corp. Unauthorized use, disclosure or reproduction is strictly prohibited.

with a missing relationship to teduglutide will be regarded as “related” to teduglutide.

#### **18.1.1.3. Serious Adverse Events**

Serious adverse events (SAEs) are those events recorded as “Serious” on the Adverse Events Form of the eCRF. Any SAE that occurs from the time of the signing of the informed consent form (ICF) through last study visit (EOS) will be captured. A summary of TESAEs by SOC and PT will be prepared, as well as summaries by event and causal relationship to study drugs. A listing of SAEs will be presented as well.

#### **18.1.2. AEs LEADING TO DISCONTINUATION OF STUDY DRUG**

AEs leading to temporary or permanent discontinuation of study drug will be identified by the “Drug Withdrawn” response for action taken with study treatment in the Adverse Events Form of the eCRF.

A listing will be provided for AEs leading to discontinuation of study drug.

#### **18.1.3. AEs LEADING TO DISCONTINUATION OF STUDY**

AEs leading to permanent discontinuation of study will be identified by the “Yes” response for the question “Did this adverse event cause the subject to be discontinued from the study?” in the Adverse Events Form of the eCRF.

A listing will be provided for AEs leading to permanent discontinuation of study.

#### **18.1.4. ADVERSE EVENTS LEADING TO DEATH**

AEs leading to Death are those events which are recorded as “Fatal” on the Adverse Events Form of the eCRF. A listing of AEs leading to death will be presented.

#### **18.1.5. ADVERSE EVENTS OF SPECIAL INTEREST**

An AE of special interest is an AE (serious or nonserious) of scientific and medical concern specific to the sponsor’s product or program and for which ongoing monitoring and immediate notification by the investigator to the sponsor is required.

The AEs of special interest that require expedited regulatory reporting include the following:

Document: \\quintiles.net\Enterprise\Apps\sasdata\SASa\sas\Shire\Teduglutide\ZXA48914\Biostatistics\Documentation\SAP\SHP633-303\_SAP\_Draft\_V1.0\_20171023

Author: [REDACTED] Version Number: Draft V1.2  
Version Date: 16Jan2018

Template No: CS\_TP\_BS016 – Revision 3  
Effective Date: 01May2012

Reference: CS\_WI\_BS005

Copyright © 2012 Quintiles Transnational Corp. All rights reserved.  
The contents of this document are confidential and proprietary to Quintiles Transnational Corp. Unauthorized use, disclosure or reproduction is strictly prohibited.

- Growth of pre-existing polyps of the colon
- Benign neoplasia of the GI tract including the hepatobiliary system
- Tumor-promoting ability (e.g., benign and/or malignant neoplasia of any kind, not limited to those of the GI or hepatobiliary system)

A review of preferred terms will be performed by a medical reviewer prior to interim and final analysis, with the identified events of special interest being documented prior to the analysis data transfer. The AEs of special interest will be presented in a listing.

## **18.2. LABORATORY EVALUATIONS**

Laboratory evaluations that are done at study site visits will be collected and processed via a central laboratory, including panels for Hematology, Clinical Chemistry, Coagulation and Urinalysis. During the tueduglutide treatment period, subjects will also have safety labs within approximately 5-7 days after a PS adjustment. Laboratory evaluations that are required at intervals that do not coincide with study site visits may be obtained by a local laboratory. The local laboratory data will be collected on the local laboratory tests form of eCRF. Laboratory evaluations to be included in the tables or listings are presented in the lab test table (Table B) below.

**Table B: Laboratory Tests**

Hematology	Chemistry	Coagulation	Urinalysis
Hemoglobin	Albumin	Prothrombin Time	Ur Blood*
Hematocrit	Alkaline Phosphatase	Prothrombin	Ur Glucose*
Platelets	Alanine Aminotransferase (ALT)	International Normalized Ratio (INR)	Ur Microscopic*
Erythrocytes	Aspartate Aminotransferase (AST)		Ur pH
RBC Morphology*	Amylase		Ur Osmolality
Leukocytes	Lipase		Ur Protein
Neutrophils	Bicarbonate		Ur Sodium
Lymphocytes	Bilirubin		Ur Specific Gravity
Monocytes	Direct Bilirubin		Ur Leukocytes
Eosinophils	Indirect Bilirubin		
Basophils	Blood Urea Nitrogen		
Neutrophils/Leukocytes	Calcium		

Document: \\quintiles.net\Enterprise\Apps\sasdata\SASa\sas\Shire\Tueduglutide\ZXA48914\Biostatistics\Documentation\SAP\SHP633-303\_SAP\_Draft\_V1.0\_20171023

Author: [REDACTED]

Version Number:  
Version Date:

Draft V1.2  
16Jan2018

Template No: CS\_TP\_BS016 – Revision 3

Effective Date: 01May2012

Reference: CS\_WI\_BS005

Copyright © 2012 Quintiles Transnational Corp. All rights reserved.

The contents of this document are confidential and proprietary to Quintiles Transnational Corp. Unauthorized use, disclosure or reproduction is strictly prohibited.

Lymphocytes/Leukocytes	Chloride		
Monocytes/Leukocytes	Cholesterol		
Eosinophils/Leukocytes	Creatinine		
Basophils/Leukocytes	C Reactive Protein		
	Glomerular Filtration		
	Rate (GFR) Schwartz		
	formula		
	Glucose		
	Gamma Glutamyl		
	Transferase (GGT)		
	Lipase		
	Magnesium		
	Phosphorus		
	Potassium		
	Sodium		
	Triglycerides		
	Uric Acid		

Note: \* lab tests with categorical results.

Lab data will be presented in SI units. The summaries will be based on central lab results only.

Quantitative laboratory measurements reported as “< X”, i.e. below the lower limit of quantification (LLQ), or “> X”, i.e. above the upper limit of quantification (ULQ), will be converted to X for the purpose of quantitative summaries, but will be presented as recorded, i.e. as “< X” or “> X” in the listings.

The following summaries will be provided for hematology, clinical chemistry and selected urinalysis laboratory data with quantitative results:

- Actual and change from baseline at Cycle x Day 1, Cycle x Week 12, Cycle x Week 24, every 12 weeks in the NTTx and End of Study
- Shift from baseline according to normal range criteria at Cycle x Day 1, Cycle x Week 12, Cycle x Week 24, every 12 week in the NTTx and End of Study
- Incidence of markedly abnormal values according to criteria defined in section [APPENDIX 3](#)
- Listing of subjects meeting markedly abnormal criteria

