## 7.3. RETESTS, UNSCHEDULED VISITS AND EARLY TERMINATION DATA

In general, for by-visit summaries, data recorded at the nominal visit will be presented. Unscheduled measurements will not be included in by-visit summaries, but can contribute to the best/worst case value where applicable. Unscheduled PS prescription adjustments carry forward until the next adjustment, and as such, may contribute to data assigned to subsequent visits.

Listings will include scheduled, unscheduled, retest and early discontinuation data.

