### 18.2.1. LABORATORY REFERENCE RANGES AND MARKEDLY ABNORMAL CRITERIA

Quantitative laboratory measurements will be compared with the relevant laboratory

Document: \\quintiles.net\Enterprise\Apps\sasdata\SASa\sas\Shire\Teduglutide\ZXA48914\Biostatistics\Documentation\SAP\SHP633-303\_SAP\_Draft\_V1.0\_20171023

Author: [REDACTED] Version Number: Draft V1.2  
Version Date: 16Jan2018

Template No: CS\_TP\_BS016 – Revision 3

Reference: CS\_WI\_BS005

Effective Date: 01May2012

Copyright © 2012 Quintiles Transnational Corp. All rights reserved.

The contents of this document are confidential and proprietary to Quintiles Transnational Corp. Unauthorized use, disclosure or reproduction is strictly prohibited.

reference ranges in SI units and categorized as:

- Low: Below the lower limit of the laboratory reference range.
- Normal: Within the laboratory reference range (upper and lower limit inclusive).
- High: Above the upper limit of the laboratory reference range.

In addition to the high and low quantitative laboratory assignments (as identified by means of the laboratory reference ranges), markedly abnormal quantitative safety (and other) laboratory assessments will also be identified in accordance with the predefined markedly abnormal criteria as presented in [APPENDIX 3](#).

The number and percentage of subjects whose post-baseline results qualify as markedly abnormal will be summarized by treatment group and the parameter. A listing will present all values for a subject and laboratory parameter if at least one post-baseline value for that subject and parameter is markedly abnormal.

Laboratory results will also be included in appendix data listings for each lab panel (chemistry, hematology, coagulation and urinalysis) by treatment, subject, visit and parameter. Values outside the normal range will be flagged. Local lab test results will only be presented in appendix data listings. Categorical test results, and pregnancy results (B-hCG, Qualitative and B-hCG, Quantitative) also will only be included in data listings.

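### The markedly abnormal laboratory count and listing exclude local results, so safety labs drawn locally after a PS adjustment cannot count

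*SAP*

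**What the plan says.** All references are to the prospective SAP (Draft V1.2).

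- **When the labs are drawn (18.2).** During the teduglutide treatment period, "subjects will also have safety labs within approximately 5-7 days after a PS adjustment".
- **Where they may be processed (18.2).** "Laboratory evaluations that are required at intervals that do not coincide with study site visits may be obtained by a local laboratory". The results are kept: "The local laboratory data will be collected on the local laboratory tests form of eCRF".
- **Which results feed the tables (18.2, text under Table B).** "The summaries will be based on central lab results only". The list of summaries that follows includes "Incidence of markedly abnormal values according to criteria defined in section" Appendix 3, and a listing of the subjects who meet those criteria.
- **What is counted (18.2.1).** "The number and percentage of subjects whose post-baseline results qualify as markedly abnormal will be summarized by treatment group and the parameter". A listing then gives all of a subject's values for a parameter once one post-baseline value is markedly abnormal.
- **What happens to local results (18.2.1).** "Local lab test results will only be presented in appendix data listings".
- **General rules.** Section 8.3 says that the safety analysis takes in all available data. Section 7.3 keeps unscheduled measurements out of by-visit summaries but says they "can contribute to the best/worst case value where applicable".

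**The concern.** A central-only rule is normal for by-visit means and shift tables, where differing assays and reference ranges would add noise. The markedly abnormal incidence is a different kind of output: it asks whether a subject crossed a fixed extreme limit at any time after baseline. Leaving out a class of samples can only remove subjects from such a count.

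The class left out is not incidental. It contains required safety labs tied to a PS change during treatment, the results are already in the eCRF, and safety is the study's primary objective (Section 3.1). The stake is that a reader of the table takes it as complete when some extreme on-treatment values sit only in an appendix. The only flag Section 18.2.1 describes for the appendix listings is for values outside the normal range, not for the Appendix 3 limits.

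**Working it through.** The plan is descriptive and states no figure for this point, so there is nothing of its own to reproduce. There are four checks.

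**1. Do the passages exclude local values from the count?** Section 18.2 makes the summaries central-only, and the markedly abnormal incidence is one of those summaries. Section 18.2.1 restricts local results to appendix listings and describes the markedly abnormal listing separately from them. On the plain reading, a local value enters neither the table nor that listing.

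**2. Do post-adjustment labs fall off-visit?** Inputs: clinic visits at weeks 1, 2, 4, 6, 9, 12, 16, 20 and 24 (Section 4.1), and windows of ±2 days for weeks 1-6 and ±4 days for weeks 9-24 (Section 7.5). For an adjustment made at one visit:

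shortest gap to next visit = 7 × (difference in weeks) − window of first visit − window of second visit

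| Adjustment at week | Next visit | Nominal gap (days) | Shortest gap (days) | Can a lab at 5-7 days meet the visit? |
|---|---|---|---|---|
| 1 | 2 | 7 | 7−2−2 = 3 | yes |
| 2 | 4 | 14 | 14−2−2 = 10 | no |
| 4 | 6 | 14 | 14−2−2 = 10 | no |
| 6 | 9 | 21 | 21−2−4 = 15 | no |
| 9 | 12 | 21 | 21−4−4 = 13 | no |
| 12 | 16 | 28 | 28−4−4 = 20 | no |
| 16 | 20 | 28 | 28−4−4 = 20 | no |
| 20 | 24 | 28 | 28−4−4 = 20 | no |

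So 7 of the 8 fall between visits and may be local. An adjustment made between visits could place its lab on a visit day, so 7 of 8 describes adjustments made at clinic visits only.

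**3. Could the criteria be applied to local values?** Appendix 3 has 18 chemistry and 5 haematology parameters, 23 in all. Six use multiples of ULN: alkaline phosphatase, ALT, AST, amylase, lipase and total bilirubin. The other 23 − 6 = 17 use absolute limits in SI units and need only unit conversion.

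**4. Direction and possible size.** For one parameter, let C be the subjects with a markedly abnormal central value and L those with a markedly abnormal local value. The table counts C, and an all-source count is C ∪ L, which is never smaller. The difference is the subjects in L but not in C.

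The documents give neither the sample numbers nor the event rates needed to size that difference. As an illustration, **assume** 10 central post-baseline samples per subject-cycle (one at each of the 10 clinic visits, weeks 1 to 28), independent samples, a per-sample probability p of a markedly abnormal value, and J local samples added. Incidence is 1 − (1 − p)^10 for central only and 1 − (1 − p)^(10+J) for all sources.

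| p (assumed) | Central only | J = 1 | J = 7 |
|---|---|---|---|
| 0.5% | 4.9% | 5.4% | 8.2% |
| 1% | 9.6% | 10.5% | 15.7% |
| 2% | 18.3% | 19.9% | 29.1% |

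The table shows that the gap could be small or material. It does not estimate the gap. The rise comes from extra sampling alone, since p is held fixed, and that bears on the objection.

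**The case against.** The case for leaving the plan alone has several parts.

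- **The rule is deliberate and consistent.** Sections 18.2 and 18.2.1 agree, and a programmer would not be in doubt. A specific rule may limit the general sentence in 8.3. This stands as far as it goes, but 8.3 carries no exception and 18.2 gives no reason for one.
- **Section 7.3 is not in conflict.** It separates scheduled from unscheduled measurements, not central from local, and it applies only where applicable. This stands. An unscheduled central result can still count, so 7.3 should not be cited as contradicted.
- **Pooling would distort comparisons.** The post-adjustment labs are required only during teduglutide treatment, while subjects in no-teduglutide (NTT) periods are seen about every 12 weeks. Adding local samples gives treated subjects, and those with more PS adjustments, more chances to cross a limit. The illustration shows incidence rising with p unchanged. This is the strongest point and it stands. A source flag does not remove it, so the main row should stay central-only.
- **Local values are still reported** in the appendix listings. True, but they are not counted and are not brought together with the subject's other markedly abnormal values.
- **Local ULNs and units may not be captured.** The SAP says that an eCRF form exists but does not describe its fields. This stands, and it limits what can be promised for the six ULN-based parameters.

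A reader might also infer more than the text allows. The SAP does not say that these labs are drawn at the time of highest risk. Nor would an affected subject be shown as normal: the table has no such category, and the subject is simply not counted. Treating one missed subject as 1/40 = 2.5% is not supported either. About 40 is expected total enrolment, including subjects who consent only to retrospective collection, whereas the table is by treatment group in the prospective safety population.

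**Conclusion.** The point holds as a minor weakness in the reporting of safety. The required post-adjustment labs mostly fall between site visits (7 of 8 for adjustments made at clinic visits in weeks 1-20) and may be processed locally. Local values are barred from the markedly abnormal incidence table and, on the plain reading, from its listing. That sits badly with the all-available-data rule in 8.3, and the count can only be too low.

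It would be going too far to say that the incidence **is** understated by a known amount. An undercount needs a subject with a markedly abnormal local value and no markedly abnormal central value for the same parameter. Local testing is permitted, not required, and its frequency is not stated, so the size cannot be derived. The documents also do not support replacing the central-only count with a pooled one, because sampling is denser during treatment.

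**What to change.** 1. Keep central-only for by-visit means, shift tables and the main row of the markedly abnormal incidence table.
2. Add a supplementary row or table labelled central plus local. Apply the Appendix 3 limits to local results converted to SI units: all 17 absolute-limit parameters, and the 6 ULN-based ones where a local ULN is recorded.
3. Include local values, with a source flag, in the markedly abnormal listing, and let a local value trigger a subject's inclusion there.
4. Align the wording: state in 8.3 that laboratory summaries are central-only except for this supplementary output, and amend the sentences in 18.2 and 18.2.1 to match.
5. Footnote the supplementary row: post-adjustment labs are required only during treatment, so it should not be compared between treated and no-teduglutide periods without that caveat.

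The cost is unit standardisation of data already collected, one extra row or table, and some between-laboratory heterogeneity. If the local form does not record ULNs, the six ULN-based parameters stay central-only and the table should say so. The SAP is still a draft, so the text change is cheap.

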### 18.2.1. LABORATORY REFERENCE RANGES AND MARKEDLY ABNORMAL CRITERIA

Quantitative laboratory measurements will be compared with the relevant laboratory

Document: \\quintiles.net\Enterprise\Apps\sasdata\SASa\sas\Shire\Teduglutide\ZXA48914\Biostatistics\Documentation\SAP\SHP633-303\_SAP\_Draft\_V1.0\_20171023

Author: [REDACTED] Version Number: Draft V1.2  
Version Date: 16Jan2018

Template No: CS\_TP\_BS016 – Revision 3

Reference: CS\_WI\_BS005

Effective Date: 01May2012

Copyright © 2012 Quintiles Transnational Corp. All rights reserved.

The contents of this document are confidential and proprietary to Quintiles Transnational Corp. Unauthorized use, disclosure or reproduction is strictly prohibited.

reference ranges in SI units and categorized as:

- Low: Below the lower limit of the laboratory reference range.
- Normal: Within the laboratory reference range (upper and lower limit inclusive).
- High: Above the upper limit of the laboratory reference range.

In addition to the high and low quantitative laboratory assignments (as identified by means of the laboratory reference ranges), markedly abnormal quantitative safety (and other) laboratory assessments will also be identified in accordance with the predefined markedly abnormal criteria as presented in [APPENDIX 3](#).

The number and percentage of subjects whose post-baseline results qualify as markedly abnormal will be summarized by treatment group and the parameter. A listing will present all values for a subject and laboratory parameter if at least one post-baseline value for that subject and parameter is markedly abnormal.

Laboratory results will also be included in appendix data listings for each lab panel (chemistry, hematology, coagulation and urinalysis) by treatment, subject, visit and parameter. Values outside the normal range will be flagged. Local lab test results will only be presented in appendix data listings. Categorical test results, and pregnancy results (B-hCG, Qualitative and B-hCG, Quantitative) also will only be included in data listings.

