## 7.2. BASELINE

Unless otherwise specified, baseline is defined as the last non-missing measurement on or prior to baseline visit in the core study TED-C13-003.

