## 7.4. STUDY CYCLE CONVENTIONS

Visits will be summarized within the associated pretreatment period or treatment cycle or no treatment period. For teduglutide treatment cycles, Cycle x Day 1, Cycle x Week 1, ..., Cycle x Week 24, Cycle x Week 25 Follow-up, Cycle x Week 26 Follow-up, Cycle x Week 27 Follow-up and Cycle x Week 28 data will be collected according to the schedule of events.

For NTT periods, NTx data will be collected approximately every 12 weeks. Data for teduglutide treatment periods and NTT periods will be presented in separate tables.

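### The incidence of markedly abnormal laboratory values does not separate subjects who already met the criterion at the core-study baseline

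*SAP*

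**What the plan says.** All references are to the prospective SAP (Draft V1.2).

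- Section 18.2, in the list after Table B, announces the output: "Incidence of markedly abnormal values according to criteria defined in section" Appendix 3.
- Section 18.2.1 gives the counting rule: "The number and percentage of subjects whose post-baseline results qualify as markedly abnormal will be summarized by treatment group and the parameter". It adds a listing of every value for a subject and parameter once one post-baseline value is markedly abnormal.
- Section 7.2 fixes the reference point: "Unless otherwise specified, baseline is defined as the last non-missing measurement on or prior to baseline visit in the core study TED-C13-003". Section 18.2 sets no other baseline for laboratory data.
- Section 18.2 tabulates change from baseline and a normal-range shift at visits that include Cycle x Day 1: "Actual and change from baseline at Cycle x Day 1, Cycle x Week 12, Cycle x Week 24" and "Shift from baseline according to normal range criteria at Cycle x Day 1". Extension Cycle x Day 1 is therefore a post-baseline visit.
- Appendix 1 makes all subjects in the treatment group or analysis set the default denominator for percentages. Section 18.2.1 does not change this.
- Section 18.1 defines treatment-emergent adverse events by onset or worsening after the first core-study dose. The laboratory count has no such condition.

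**The concern.** Incidence normally means subjects who did not have the condition and then developed it. The rule in 18.2.1 counts subjects who meet the criterion at any time after the core baseline, whatever their baseline status. That is a period prevalence. A stable abnormality present before the first core-study dose would not be a treatment-emergent adverse event under 18.1, yet it enters the laboratory incidence.

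Long-term safety is the primary objective (section 3.1), and the interim analysis supports a regulatory submission (section 5.1). This is the only planned laboratory summary table that uses the Appendix 3 limits. If some children already met a limit at the core baseline, its percentage mixes them with children who became markedly abnormal later, and the table gives no way to tell them apart.

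**Working it through.** The SAP gives no rate for this table, so there is no planned figure to reproduce. The check has two parts.

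**1. Does the rule count a pre-existing case?** Take a subject who meets an Appendix 3 criterion at the core baseline and at a later extension visit.

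- Numerator: the later value is post-baseline under 7.2 and markedly abnormal, so 18.2.1 counts the subject.
- Denominator: Appendix 1 keeps the subject in.
- Shift table: it classifies values against the laboratory reference range. A baseline in the high category may be just above the range or beyond the Appendix 3 limit (for ALT, more than 8 times the upper limit of normal). The table cannot tell which.
- Listing: it shows all the subject's values, so the case can be found by hand, but the tabulated number and percentage stay mixed.

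**2. How much could it matter?** Let b be the share markedly abnormal at core baseline, r the share of those who are so again afterwards, and i the rate of becoming so among the rest. All three are assumptions; the SAP gives none of them.

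Rate under the current rule = b × r + (1 − b) × i. Rate among subjects at risk = i.

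N = 40 is the approximate expected enrolment in section 4.1. One persistent baseline case adds 1/40 = 2.5 percentage points.

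With i = 5%:

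| b | Current rule, r = 0.5 | Current rule, r = 1 | At-risk rate |
|---|---|---|---|
| 0% | 5.00% | 5.00% | 5% |
| 5% | 7.25% | 9.75% | 5% |
| 10% | 9.50% | 14.50% | 5% |
| 20% | 14.00% | 24.00% | 5% |

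Example for b = 10%, r = 1: 0.10 × 1 + 0.90 × 0.05 = 0.145.

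With i = 0 and r = 1, one to eight persistent cases out of 40 (b = 2.5% to 20%) give 2.5% to 20% in a table where no subject became markedly abnormal after baseline.

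The 40 includes subjects who consent to retrospective collection only, and the table is by treatment group, so a column may hold fewer subjects. Each case then adds 100/n points; for an assumed column of 20, that is 100/20 = 5 points.

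**The case against.** The strongest reply is that counting any post-baseline value beyond a limit is a recognised descriptive convention. The SAP never calls these values new or treatment-emergent. The analysis is descriptive, with no testing and no comparison between groups. The listing shows every value for each counted subject, which is workable with about 40 children. The Appendix 3 limits also lie far from normal (sodium below 120 mmol/L, hemoglobin below 70 g/L), so few or no children may meet them at baseline. All of this stands and limits the consequence. It does not change the fact that the count is labelled incidence and leaves baseline status out.

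A reader might go further and infer that Cycle x Day 1 values are pre-treatment, are reported as arising on drug in that cycle, and should be excluded. The SAP does not support this:

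- Sampling before the dose on Cycle x Day 1 is stated for the antibody sample only (18.4). For safety laboratory tests it is an inference.
- Section 7.4 places the visit in the cycle ("For teduglutide treatment cycles, Cycle x Day 1, Cycle x Week 1") and says "Data for teduglutide treatment periods and NTT periods will be presented in separate tables". But 18.2.1 summarises by treatment group and parameter, and nothing defines a markedly abnormal count per cycle. The table shells are in a separate file.
- TED/TED subjects took teduglutide in the core study (section 6). A value that is normal at core baseline and markedly abnormal at Cycle x Day 1 arose after first exposure. Calling it pre-existing could hide an effect of earlier treatment. Counting it agrees with the core-study anchor that 18.1 uses for adverse events.

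**Conclusion.** The point holds in a limited form. The figure labelled incidence includes subjects who were already markedly abnormal at the core-study baseline and are so again later, and no summary table separates them. Its size is unknown: 2.5 percentage points per persistent baseline case if the denominator is 40, more in a smaller treatment-group column, and zero if no child met a limit at baseline. The percentages in the worked table rest on assumed values of b, r and i and show direction and scale only.

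The SAP does not support saying that it reports pre-existing abnormalities as new under treatment, or that Cycle x Day 1 results should be removed. This is a worthwhile, nearly free correction to a descriptive table that serves the primary safety objective. It does not invalidate the analysis.

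**What to change.** In 18.2.1, for each parameter and for each direction (below the lower or above the upper Appendix 3 limit), report two rows:

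- (a) subjects not markedly abnormal at core baseline who become so afterwards; the denominator is subjects not markedly abnormal at core baseline with at least one post-baseline value;
- (b) subjects already markedly abnormal at core baseline who are so again afterwards.

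State where subjects with no core baseline value are shown, for example as a separate count.

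Keep abnormalities first seen at Cycle x Day 1 in the overall count after core baseline. If a treatment-cycle table is produced, flag values first seen at Cycle x Day 1 separately from later values in that cycle, and do not remove them.

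The cost is SAP wording, one flag and one extra row per parameter, with slightly smaller denominators in row (a): with N = 40 and b = 10%, 36 instead of 40. The planned change-from-baseline tables already need the core baseline values, so no new data are required.
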